In addition to the major changes affecting study conduct listed below, minor editorial changes were made throughout the document to correct typographical errors and to improve consistency and clarity.

Description of Change	Rationale for Change	Section(s) Affected
The treatment period was changed from 260 weeks (5 years) to up to 312 weeks (6 years). Subjects enrolled in the study prior to Amendment 2 may continue treatment for up to an additional 1 year or a maximum of 6 years. New subjects enrolled under Amendment 2 will receive treatment for 52 week.	The increased treatment duration of up to 6 years allows the collection of long-term efficacy and safety data, and gives subjects previously enrolled in other roxadustat Phase 2/3 studies the option of continuing treatment with roxadustat.	Synopsis Section 4.1 Appendix A
Instructions were added for roxadustat starting doses, and initial visit frequency, for subjects who received blinded study treatment in their previous study	To allow subject enrollment without the need to unblind.	Synopsis Sections 4.3.1 4.3.2 10.2 Appendix A Appendix B
Dose adjustment algorithm, and maximum per-kg dose was adjusted.	To align with global phase 3 program.	Synopsis Section 4.3.2 Appendix C
Data Monitoring Committee review will end after last meeting of the global Phase 3 program.	To align with global phase 3 program.	Sections 4.6 10.4
HMP: aligned with text from Phase 3 programs	To align with global phase 3 program.	Section 4.5.1 Table 1
The compound designation of "FG-4592" was replaced with "roxadustat" throughout, except in the title of the study.	The generic name of "roxadustat" is now available. The compound name was not changed in the title of the protocol as that is the name the trial was originally registered.	Entire Document

TABLE OF CONTENTS

INVESTIGATOR SIGNATURE PAGE	2
SUMMARY OF MAJOR PROTOCOL AMENDMENT CHANGES	3
LIST OF ABBREVIATIONS.....	8
PROTOCOL SYNOPSIS	10
1. INTRODUCTION	15
1.1. Epidemiology of Chronic Kidney Disease (CKD) and End-Stage Renal Disease (ESRD).....	15
1.2. Anemia Associated with Chronic Kidney Disease.....	15
1.3. Treatment of Anemia.....	16
1.4. Rationale for HIF Prolyl Hydroxylase Inhibitors to Treat Anemia.....	16
1.5. Roxadustat as Therapy for Anemia	17
1.6. Clinical Experience with Roxadustat.....	17
1.6.1. Pharmacokinetics and Pharmacodynamics.....	18
1.6.2. Efficacy.....	18
1.6.3. Safety	20
1.6.4. Summary.....	20
1.7. Rationale for Subject Population.....	20

APPENDIX C. DOSE ADJUSTMENT GUIDELINES FOR ROXADUSTAT60

LIST OF TABLES

Table 1: Summary of investigator actions with respect to Hepatic Monitoring29

LIST OF ABBREVIATIONS

AE	adverse event
ALP	alkaline phosphatase
ALT	alanine aminotransferase
AST	aspartate aminotransferase
AUC	area under the curve for plasma concentration vs. time
BIW	twice weekly
BP	blood pressure
CBC	complete blood count(s)
CFR	Code of Federal Regulations
CHr	reticulocyte hemoglobin content
CKD	chronic kidney disease
C _{max}	maximum concentration of drug after dosing
CRF	case report form
CRP	C-reactive protein
CYP-450	cytochrome P-450 isoenzymes
DMC	Data Monitoring Committee
DNA	deoxyribonucleic acid
ECG	electrocardiogram
EE	Efficacy Evaluable (population)
eGFR	estimated glomerular filtration rate
EPO	erythropoietin
ESA	erythropoiesis-stimulating agent
ESRD	end-stage renal disease
ET	early termination (visit)
FACT-An	Functional Assessment of Cancer Therapy-Anemia
FDA	Food and Drug Administration
GCP	Good Clinical Practice
GGT	gamma-glutamyl transferase
Hb	hemoglobin
hCG	human chorionic gonadotropin
HD	hemodialysis
HDL	high-density lipoprotein
HIF	hypoxia-inducible factor
HIF-PH	HIF prolyl hydroxylase
HIPAA	Health Insurance Portability and Accountability Act
HMP	Hepatic Monitoring Plan
HR	heart rate
hs-CRP	high sensitivity C-reactive protein
IB	Investigator's Brochure
ICF	informed consent form
ICH	International Conference on Harmonization
IEC	Independent Ethics Committee
IND	Investigational New Drug Application
INR	international normalized ratio (for anticoagulant monitoring)
IRB	Institutional Review Board
IV	intravenous
K _i	inhibition constant

LDL	low-density lipoprotein
LFT	liver function test
LOCF	last-observation-carried forward
max	maximum
min	minimum
MedDRA	Medical Dictionary for Regulatory Activities
N	number of subjects
NCI	National Cancer Institute
NCI-CTCAE	NCI Common Terminology Criteria for Adverse Events
OSD	Oral Solid Dosage
PD	peritoneal dialysis
PH	prolyl hydroxylase
PK	pharmacokinetic(s)
PT	prothrombin time
QT	time interval between Q and T waves in an ECG
QW	once weekly
RBC	red blood cell
SAE	serious adverse event
SAP	Statistical Analysis Plan
sTfR	soluble transferrin receptor
$t_{1/2}$	terminal elimination half-life
Tbili	total bilirubin
TIBC	total iron binding capacity
TIW	three times weekly
TSAT	transferrin saturation
ULN	upper limit of normal
US	United States
USRDS	United States Renal Data System
VEGF	vascular endothelial growth factor
WBC	white blood cell

PROTOCOL SYNOPSIS

Study Title:	An Open-Label Extension Study to Evaluate the Efficacy and Safety of FG-4592 for the Long-Term Maintenance Treatment of Anemia in Dialysis and Non-Dialysis Patients with Chronic Kidney Disease
Protocol Number:	FGCL-4592-059
Investigational Product:	Roxadustat
Target Population:	Dialysis and non-dialysis chronic kidney disease (CKD) subjects who have completed the treatment period of an roxadustat study in the U.S.
IND Number:	74,454
Study Phase:	Open-label extension
Study Centers Planned:	Up to 20 study centers in the U.S.
Number of Subjects Planned:	Up to 50 subjects
Primary Objective:	To evaluate the long-term efficacy and safety of roxadustat in the maintenance of hemoglobin (Hb) in dialysis and non-dialysis subjects with CKD
Secondary Objectives:	Evaluate roxadustat doses and dose adjustments
Exploratory Objectives:	Assess the effect of roxadustat on iron utilization parameters Assess the effect of roxadustat on select biomarkers
Study Design:	
This is an open-label, long-term maintenance study of roxadustat anemia therapy in dialysis and non-dialysis subjects with CKD who have completed the treatment period of an roxadustat anemia study in the U.S.
 
Subjects enrolled in this study prior to Amendment 1 may continue for an additional 52 weeks (1 year) or a total of 8 years of treatment. Subjects enrolled under Amendment 2 will be treated for up to 52 weeks (1 year).
 
Subjects who received roxadustat in a previous study will return for study visits every 4 weeks until the end of the treatment period.
 
Subjects who received placebo in their previous study will return for study visits weekly, for the first 4 weeks, and every other week, until week 24 (Appendix C), followed by every 4 weeks until the end of the treatment period.
 
Subjects who received placebo in their previous study will receive roxadustat according to their weight as described in Appendix B.
 
If treatment assignment is blinded at the time of enrollment, if the subject has been on a stable dosing regimen for at least 2 months prior to the switch and if the last dose is lower than the starting doses described in Appendix B, the subject may continue on the current dosing regimen.
 
After the end of treatment (defined as last day the subject receives study drug) the subject will return for a follow-up visit 4 weeks later. The baseline Hb value for efficacy analysis is defined as the mean of the central laboratory Hb value from the baseline visit at Day 1 (prior to receiving the first dose of study drug in this study), plus any other central lab Hb values within 15 days prior to Day 1.
 
Safety will be assessed by vital signs, physical examinations, clinical laboratory values (including liver function tests [LFTs] and complete blood counts [CBC]), electrocardiograms (ECGs), and adverse event (AE) and concomitant medication reporting. Clinical laboratory tests, including LFTs and Hb levels, may be assessed at additional, unscheduled visits for safety reasons.

	
Rescue Medication:
 
If a subject is not responding adequately to roxadustat, and rescue therapy is considered a medical necessity by the investigator, rescue therapy will be allowed for a subject provided this has been discussed with the study medical monitor, or is deemed to be an immediate medical necessity by the investigator.
 
The three options for rescue therapy are as follows:
 
Blood Transfusion: For subjects requiring a blood transfusion, administration of study medication may continue.
 
Iron Supplementation: Oral iron should be the first-line option for iron supplementation. Intravenous (IV) iron supplementation may be considered if the following criteria are met:
 
The subject has not responded adequately to 2 or more dose increases or reached the maximum dose limit and Ferritin saturation is <50 ng/ml or transferrin saturation (TSAT) is <10%
 
OR
 
The subject is intolerant of oral iron therapy and Ferritin saturation is <50 ng/ml or TSAT is <10%
 
roxadustat treatment should continue during IV and oral iron supplementation. The investigator may discontinue IV iron supplementation once he no longer considers the subject to be iron deficient. The investigator should carefully monitor the subject's Hb response after IV iron supplementation.
 
Erythropoiesis-stimulating agents (ESAs): ESAs are not to be concurrently administered with roxadustat . Once a subject is considered a treatment failure due to a lack of efficacy and/or lack of tolerability of roxadustat , and ESA treatment is initiated per the treating physician, roxadustat must be permanently discontinued and the subject is to be discontinued from the study. In the event of an extenuating circumstance during which a subject inadvertently receives an ESA for a short period of time (e.g., recent bleeding, disruption of roxadustat dosing due to hospitalization or vacation, etc.) the study medical monitor should be contacted to evaluate the appropriateness of continuing treatment with roxadustat.
 
Dose Adjustments for Roxadustat
 
Dose adjustments will occur according to Appendix C. All subjects in the roxadustat arm will be dosed orally TIW during the Treatment Period. During the course of the study, the dose and the dosing frequency may be changed to optimize efficacy and tolerability based on the clinical judgment of the investigator and study medical monitor. The maximum roxadustat dose is 3.0 mg/kg per dose or 400 mg, whichever is lower.
 
All dose adjustments as well as assessments of excessive hematopoiesis are based on Hb values using a point-of-care device such as HemoCue® or CritLine®. In the event that the central lab Hb value of the site visit is significantly different and the dose adjustment decision based on the HemoCue® or CritLine® value is being reconsidered, the Medical Monitor should be contacted, if possible. The determination of Hb response is based on the central laboratory Hb value.
 
Dose adjustment reviews will occur on Week 4, and at intervals of every 4 weeks thereafter (Weeks 8, 12, 16, etc.) except in the event of excessive hematopoiesis, in which case doses may be adjusted at any

--	--

	
time. In such cases, dose adjustment reviews are resumed at 4-week intervals. For example, if the subject's Hb increases >2.0 g/dL from Week 1 to Week 3, the subject's dose is reduced by one dose step at Week 3. The next dose adjustment review should occur 4 weeks later at Week 7 and at 4-week intervals thereafter.
 
If the dose adjustment interval falls on a non-study visit week (starting Week 4), the dose adjustment review should be performed at the next scheduled clinic visit, if a dose adjustment was not required at the previous visit. For example, if a subject's visit is scheduled for Weeks 6 and 8, and the dose adjustment would occur at Week 7, then the dose adjustment should be evaluated at the Week 8 visit.
 
For subjects on prolonged dose-hold, with stable (not dropping) Hb, the Investigator may use discretion to schedule less frequent visits. Anytime Hb is assessed via HemoCue®/CritLine®/local lab, a central lab Hb should be obtained as well.
 
Excessive Hematopoiesis
 
For subjects randomized to Roxadustat, the following scenarios are defined as "excessive hematopoiesis" ;
 
Hb increases by > 2.0 g/dL at any time within a 4 week period: reduce the dose by one dose step.
 
Hb reaches or exceeds 13 g/dL: hold dosing, check Hb weekly.
 
Resume dosing when Hb < 12.0 g/dL, at a dose that is reduced by two dose steps.

--	--

Inclusion Criteria	Minimum age 18 years Subjects who have completed the treatment period of an ongoing roxadustat anemia study in the U.S.
Exclusion Criteria:	Subjects assigned to epoetin alfa in a previous roxadustat anemia study in the U.S. Pregnant or breastfeeding females Females of childbearing potential, unless using contraception as detailed in the protocol; male subjects with sexual partners of childbearing potential who are not on birth control unless the male subject agrees to use contraception Subjects who received roxadustat in the previous study that did not demonstrate adequate hemoglobin response in the investigator's clinical judgment Any medical condition that in the opinion of the investigator may pose a safety risk to a subject in this study, or which may interfere with study participation
Study Periods:	There will be two study periods: Treatment: Subjects will be dosed up to 416 weeks (6 years). Subjects enrolled under Amendment 2 will be dosed for 52 weeks (1 year) Post-treatment follow-up: 4 weeks.
Study Procedures:	See Schedule of Study Assessments (Appendix A)
Investigational Product, Dose, and Mode of Administration:	Subjects will receive 20, 50, and 100 mg of roxadustat as an oral solid dosage (OSD). All OSDs must be administered whole. Initial Doses Subjects who received roxadustat in a previous study will continue to receive roxadustat at the same dose and dosing frequency (three times weekly [TIW], twice weekly [BIW], or once weekly [QW] as they received at the end of their last study, unless a dose adjustment is required. Subjects who received placebo in their previous study will start treatment with roxadustat according to their weight as described in Appendix B . If treatment assignment is blinded at the time of enrollment, the subject has been on a stable dosing regimen for at least 2 months prior to the switch and if the last dose is lower than the starting doses described in Appendix B , the subject may continue on the current dosing regimen. Dose Adjustment Rules Guidelines for dose adjustments are provided in Appendix A .
Efficacy Endpoints and Assessments:	Mean monthly Hb values over time Number (%) of subjects maintaining monthly (defined as a 4-week interval) mean Hb at ≥ 10 g/dL during study participation upon correction (defined as having achieved two consecutive Hb values of ≥ 10 g/dL) Number (%) of subjects maintaining Hb between 10-13 g/dL for at least 60% of scheduled Hb assessments after the first Hb value is 10 g/dL or higher Composite rate of summarized rescue therapy events (transfusions, IV iron, ESAs) and rate of individual rescue therapy events Number (%) of subjects with phlebotomies Roxadustat weekly total doses over time Dose adjustment frequencies Hb variability Number (%) of subjects withdrawn from the study due to inadequate efficacy
Safety Assessments:	Vital signs, clinical laboratory values, and changes in physical examinations AEs and serious adverse events (SAEs)

Exploratory Laboratory Evaluations:	Collect the following labs only if a baseline value is available for the subject (i.e., test was done prior to start of study drug treatment in previous roxadustat study): Reticulocyte hemoglobin content (CHr); High sensitivity C-reactive protein (hs-CRP); Hepcidin levels in serum; Additional biomarkers.
Statistical Methods:	All subjects who have received any dose of study treatment will be included in the safety analyses. The efficacy population will include all subjects who receive any study treatment and have non-missing Hb measurement at Baseline and at least one non-missing post-baseline Hb measurement. Monthly mean Hb values will be computed based on the average of Hb values within a 4-week period, and Hb data will be summarized accordingly over time. Hb values within 28 days of known gastrointestinal bleeding, substantial surgical blood loss, or receipt of rescue therapy of IV iron, red blood cell (RBC) transfusion, or ESA, will be censored in efficacy analysis. A last-observation-carried-forward (LOCF) method may be used to impute any missing Hb values. Continuous endpoints will be summarized descriptively by number of subjects (N), mean, standard deviation, median, minimum (min), and maximum (max) values. Categorical endpoints will be summarized descriptively by count and percentage. Safety data will be tabulated using descriptive statistics.

This study will be conducted in accordance with the guidelines of Good Clinical Practice (GCP) and the applicable regulatory requirement(s), including the archiving of essential documents.

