3. ENDPOINTS AND ASSESSMENTS

3.1. Efficacy

The efficacy endpoints in this study are:

- Mean monthly Hb values over time;
- Number (%) of subjects maintaining monthly (monthly defined as a 4-week interval) mean Hb at ≥ 10 g/dL during study participation upon correction (correction is defined as having achieved 2 consecutive Hb values of ≥ 10 g/dL);
- Number (%) of subjects maintaining Hb between 10-13 g/dL for at least 60% of scheduled Hb assessments after the first Hb value is 10 g/dL or higher.
- Composite rate of summarized rescue therapy events (transfusions, IV iron, ESAs) and rate of individual rescue therapy events;
- Number (%) of subjects with phlebotomies;
- Roxadustat weekly total doses over time;
- Dose adjustment frequencies;
- Hb variability;
- Number (%) of subjects withdrawn from the study due to inadequate efficacy.

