4.3.2. Dose Adjustments

Guidelines for dose adjustments are provided in C. In general:

- The Hb thresholds for dose adjustments are < 10 g/dL for dose increases and \geq 12 g/dL for dose reductions
- Dose adjustment rules are based on changes in Hb values over 4 weeks and whether the Hb target has been reached or exceeded.
- Dose increases and decreases are pre-set at the dose steps described in [Appendix A](#).
- The maximum dose is 3.0 mg/kg.
- The time interval between dose adjustment reviews should be 4 weeks, except in the event of excessive hematopoiesis (when the subject's dose should be reduced), or rapidly declining Hb (when the subject's dose should be increased). For example, even if a subject's dose is not increased or decreased following a dose adjustment review visit, the next dose adjustment review will be 4 weeks after the last dose adjustment review.
- For subjects who received placebo in their previous study, no dose adjustment will occur from Weeks 1 through 4 except in the event of excessive hematopoiesis or rapidly declining Hb.
- For subjects who received roxadustat, or blinded study drug, and on a stable dose for the past 2 months, in a previous study, dose adjustment review will occur 4 weeks from the last dose adjustment review in the previous study.
- During the course of the study, the dose and the dosing frequency may be changed to optimize efficacy and tolerability based on the clinical judgment of the investigator and study medical monitor.

In the event of an extenuating clinical circumstance (e.g., recent bleeding, disruption of dosing due to hospitalization or vacation, etc.), the investigator may dose a subject outside of the dose adjustment parameters provided this has been discussed with the study medical monitor.

Dose Frequency Adjustments should be done according to [Appendix C](#).

Dose Adjustment for Excessive Hematopoiesis

At any time during the treatment period, if Hb increases by > 2.0 g/dL in 2 weeks that is not due to an RBC transfusion the dose should be reduced by one dose step ([Appendix A](#)).

If there are clinical concerns for a subject's excessively high Hb value outside the dose adjustment intervals (as described in [Appendix A](#)), the investigator may adjust the dose immediately; the investigator may also decide to perform a therapeutic phlebotomy in addition to the dose adjustments—these situations should be documented and discussed with the study medical monitor whenever possible.

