4.4.3. Rescue Medication

If a subject is not responding adequately to roxadustat, and rescue therapy is considered a medical necessity by the investigator, rescue therapy will be allowed for a subject provided this has been discussed with the study medical monitor, or is deemed to be an immediate medical necessity by the investigator.

The three options for rescue therapy are as follows:

1. Blood transfusion: For subjects undergoing rescue therapy with transfusion, administration of study medication may continue.
2. Iron supplementation: Oral iron should be the first-line option for iron supplementation. IV iron supplementation may be considered if the following criteria are met:

- The subject has not responded adequately to 2 or more dose increases or reached the maximum dose limit and
- Ferritin saturation is <50 ng/ml **or** transferrin saturation (TSAT) is <10%

OR

- The subject is intolerant of oral iron therapy and
- Ferritin saturation is <50 ng/ml **or** TSAT is <10%

Roxadustat treatment should continue during oral and IV iron supplementation. The investigator may discontinue IV iron supplementation once he no longer considers the subject to be iron deficient. The investigator should carefully monitor the subject's Hb response after the IV iron supplementation.

3. ESAs: ESAs are not to be concurrently administered with. Once a subject is considered a treatment failure due to a lack of efficacy and/or lack of tolerability, and ESA treatment is initiated per the treating physician, roxadustat must be permanently discontinued and the subject also is to be discontinued from the study. In the event of an extenuating circumstance during which a subject inadvertently receives an ESA for a short period of time (e.g., recent bleeding, disruption of dosing due to hospitalization or vacation, etc.), the study medical monitor should be contacted to evaluate the appropriateness of continuing treatment with roxadustat.

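### The protocol censors Hb after bleeding and rescue but not after therapeutic phlebotomy, which can flatter the 10-13 g/dL endpoint and the Hb range tables, probably by little

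*Protocol*

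**What the plan says.** **Censoring rule.** It appears in the Protocol Synopsis under Statistical Methods. The first part covers "Hb values within 28 days of known gastrointestinal bleeding, substantial surgical blood loss, or receipt of rescue therapy of IV iron"; it ends with "red blood cell (RBC) transfusion, or ESA, will be censored in efficacy analysis". Protocol 10.6.2 (Efficacy Analyses) does not repeat it. The same Synopsis entry adds: "A last-observation-carried-forward (LOCF) method may be used to impute any missing Hb values".

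**Phlebotomy.** For an excessively high Hb, Protocol 4.3.2 says that "the investigator may also decide to perform a therapeutic phlebotomy in addition to the dose adjustments". Protocol 4.4.3 opens its list with "The three options for rescue therapy are as follows" and names transfusion, iron and ESAs, so phlebotomy does not enter the censoring rule as rescue.

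**Endpoints.** Protocol 3.1 includes "Number (%) of subjects maintaining Hb between 10-13 g/dL for at least 60% of scheduled Hb assessments", counted after the first value of 10 g/dL or higher. It also has a maintenance endpoint with a floor of 10 g/dL and no ceiling ("Number (%) of subjects maintaining monthly (monthly defined as a 4-week interval) mean Hb"), and a separate count, "Number (%) of subjects with phlebotomies". Protocol 10.6.2 plans tables of Hb values within, above and below ranges between 11.0 and 13.0 g/dL.

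**SAP.** Section 10.1 summarises efficacy on observed data. No event triggers censoring of Hb anywhere in the SAP. Sections 4.1 and 10.1 keep the endpoint of mean Hb at 10 g/dL or above; they do not list the 10-13 g/dL endpoint or the phlebotomy count. Section 3 reports 15 subjects entered.

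**The concern.** The censoring list evidently aims to remove Hb values disturbed by something other than roxadustat, and it already treats blood loss as such a disturbance. Deliberate blood removal acts on Hb in the same direction. As written, low values after unplanned blood loss are dropped, while values lowered from above range by planned removal are kept and can score as in range.

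The omission is not explained by phlebotomy being unforeseen, since the protocol counts it as an endpoint. Protocol 11.2.1 and 11.3.6 also exempt out-of-range Hb from adverse event reporting on the ground that the efficacy analyses will capture it. Those analyses are therefore where overshoot is meant to be seen, and an in-range score after phlebotomy shortens its apparent duration.

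**Working it through.** The plan gives no power calculation and no phlebotomy frequency, so there is no stated figure to reproduce. The check has two parts: direction by endpoint, then sensitivity of the 60% rule.

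**1. Direction of the effect when post-phlebotomy values are kept**

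| Measure | Upper limit? | Effect |
|---|---|---|
| 10-13 g/dL at 60% or more of assessments (Protocol 3.1) | Yes | Can turn an out-of-range value into an in-range one: favourable |
| Hb range tables (Protocol 10.6.2) | Yes | Moves values from above range to in range: favourable |
| Mean Hb over time | No | Lowers the mean |
| Mean Hb at 10 g/dL or above | No | Overshoot already counted as success; a lower value can only count against the subject |
| Hb variability | No | Direction not determined |

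For scale on mean Hb, assume that one phlebotomy lowers Hb by 0.5 to 1.0 g/dL (an assumption; the documents give no figure). One affected subject among 15 then shifts the visit mean down by 0.5/15 = 0.03 to 1.0/15 = 0.07 g/dL.

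**2. Sensitivity of the 60% rule**

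Inputs: the 60% cut (Protocol 3.1); four-weekly visits for 52 weeks, 52/4 = 13 assessments; four-weekly visits for the maximum of 312 weeks (Protocol 4.1), 312/4 = 78; two-weekly visits for 52 weeks, 52/2 = 26. Take a subject who just passes, with x = the smallest whole number not below 0.6 × k. Assume that one in-range value falls within 28 days after a phlebotomy. Censoring it gives (x − 1)/(k − 1).

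| k | 0.6 × k | x | As written | One value censored |
|---|---|---|---|---|
| 13 | 7.8 | 8 | 8/13 = 61.5%, maintained | 7/12 = 58.3%, not maintained |
| 26 | 15.6 | 16 | 16/26 = 61.5%, maintained | 15/25 = 60.0%, still maintained |
| 78 | 46.8 | 47 | 47/78 = 60.3%, maintained | 46/77 = 59.7%, not maintained |

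At two-weekly visits two values can fall in the window: 14/24 = 58.3%, not maintained. Subjects away from the cut do not change status. One reclassified subject is 1/15 = 6.7 percentage points of those entered, or 1/50 = 2.0 points of the planned maximum.

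**3. Two details that decide the answer**

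- *LOCF.* If the censored value is treated as missing and the pre-phlebotomy overshoot is carried forward, 8/13 becomes 7/13 = 53.8%, and mean Hb at that visit is pushed up.
- *Window direction.* The rule says within 28 days of the event, without stating before or after. If the window ran both ways and also removed one out-of-range value before the phlebotomy, 8/13 would become 7/11 = 63.6%, still maintained, and the overshoot would disappear from the analysis.

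**The case against.** The strongest case against has five parts.

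- **The SAP analysis is not affected in this way.** It keeps values after bleeding, transfusion and phlebotomy alike, so the asymmetry is absent, and the 10-13 g/dL endpoint is not listed. This stands. It confines the specific bias to the protocol's analysis. For the SAP the gap is wider and different: the rule and the phlebotomy count are missing. The SAP places table specifications in a separate document, so a table could exist there, but the plan does not commit to one.
- **The fall in Hb has mixed causes.** Protocol Appendix C calls for a dose hold at 13 g/dL or above, and phlebotomy comes on top of dose adjustment. Some of the fall would occur anyway. This stands, and it is why such a value can be credited neither wholly to dosing nor wholly to phlebotomy.
- **Phlebotomies are counted separately in the protocol.** This gives partial transparency, but the count does not alter any Hb endpoint.
- **The size rests on assumptions.** Frequency is unknown and could be zero among 15 subjects. This stands.
- **Censoring has its own cost.** It could delete a post-phlebotomy value below 10 g/dL and so hide a failure. This stands, and the removed values should therefore be listed.

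A reader might infer that the trial's Hb results in general credit roxadustat with control achieved by phlebotomy. The documents do not support that. Favourable bias is shown only where there is an upper limit; mean Hb moves down, and the endpoint at 10 g/dL or above cannot gain a success.

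**Conclusion.** The omission is real and inconsistent with the protocol's own treatment of blood loss. It favours the result only on the 10-13 g/dL endpoint and the Hb range tables of the protocol analysis. The effect is probably small and cannot be quantified. It needs a subject who was phlebotomised, has a later in-range value inside 28 days, and sits close to the 60% cut. If one such subject exists, the endpoint moves by 6.7 points with 15 subjects. The point is minor, but worth correcting because the correction is cheap and because the SAP as it stands contains neither the censoring rule nor the phlebotomy count that would let a reader judge the matter.

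**What to change.** These changes concern only which Hb values enter the analysis.

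1. Add therapeutic phlebotomy to the censoring list, applied only to the 28 days after the event, so that the pre-phlebotomy overshoot stays in.
2. Carry the full list into the SAP Hb summaries, or report those summaries with and without the affected values.
3. State that LOCF is not applied to values censored for phlebotomy, or show the result both ways.
4. Restore the phlebotomy count in the SAP, and the 10-13 g/dL endpoint if it is to be reported.
5. Give the number of Hb values removed for this reason and list them, including any below 10 g/dL.

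The cost is a short addition to the rule, a matching paragraph in the SAP, one listing, and the loss of a few Hb values. The in-range percentage may come out slightly lower.
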